7.2 Sample Size

These sample size estimates are for the GLOBAL-BALLAD collaboration.

It is estimated that survival rates and incidence of the various stage groups are:

Stage I (assumed incidence 10%): 55% 5 year overall survival.

Stage II (assumed incidence 45%): 45% 5 year overall survival.

Stage III (assumed incidence 45%): 30% 5 year overall survival.

R0 resected Stage IV (assumed incidence 0-5%): less than 30% 5 year overall survival.

Based on the experience in CRC, it is assumed that these 5 year OS rates are the same as 3 year DFS rates. We anticipate that there will be proportionately more patients with stage I-II SBA in group I and more stage III/IV SBA in group 2, and hence the 3 year DFS rate for group 1 patients will be approximately 45% and group 2 will be approximately 40%.

The hazard ratio (HR) for DFS observed in the QUASAR study was 0.78 and in the MOSAIC study was 0.77. This trial will target a HR of 0.775 for both the adjuvant chemotherapy and oxaliplatin questions, corresponding to a ~9% improvement in 3-year DFS. The number of DFS events required to detect this HR at the 20% 1-sided level of statistical significance is 287 (90% power) or 190 (80% power). The table below shows the number of patients required for both the adjuvant (Group 1) and Oxaliplatin (Group 2) questions assuming accrual over 5 years and 2 years of subsequent follow-up (incorporating one interim assessment for futility once half the events have been observed using Lan-DeMets spending function with an O'Brien-Fleming type boundary).

Total	580	880
Oxaliplatin Question	280	425
Adjuvant Question	300	455
	80% Power	90% Power

Version 6: 16th July 2021 Page 55 of 87

The total sample size requirement for both studies at 80% power is 3.9% of total incidence and for 90% power is 5.9%. Of course this total sample size requirement as a percentage of incidence would be further reduced depending on the proportion of patients who are randomised between the chemotherapy options in the adjuvant question (these calculations assume that no such patients are randomised).

The initial intention was to achieve 90% power for both questions, but consideration was given to the realities of recruitment meaning that only the sample size requirements for 80% power may have been realistic. Hence, the minimum sample size required was estimated to be 580 patients and the maximum was 880 patients (assuming no patients are randomised to the Oxaliplatin question from those recruited to the Adjuvant question).

The target recruitment for BALLAD UK was planned to be 120 patients.

Recruitment to the study has been and continues to be challenging, however the study design is as permissive as is reasonable in this setting in terms of the power and significance level, so adjusting the sample size calculations is not appropriate. Calculations have been performed to estimate the final resultant power for both questions should the study continue at the rate observed since the study re-opened to recruitment following suspension due to the COVID-19 pandemic, and if recruitment were to increase to the highest observed rate of recruitment for that question.

Question 1 (Observation versus Chemotherapy) Recruitment 300 280 Original target recruitment over 5 years (n=300) 260 Revised target recruitment over 7 240 years (n=260) 220 9 Recruitment due to COVID-200 Patients 180 Į 140 Cumulative 120 Suspension in Estimated "best" final recruitment (n=114) 100 80 Estimated "worst" final 60 recruitment (n=95) Overall (n=77) 40 UK (n=10)

Question 1: Observation versus Chemotherapy

Version 6: 16th July 2021

01.580.16 Ol Way 16 01.NOV.16 01.580-17 OLWAY I 01-818-17 Ol.Nov.17 01.580.18 01.Nav.18 01-AUE-18

20

Page 56 of 87

01.NOV-18

01.Feb.19 01.1184.19 01-818-19 01.NOV.19

01.580.20

01.Nav.20 01-AU8-20

01.Nov.20

[figure not shown]
01.580.22 01.May.21 01-818-22 01.NOV.21

France (n=9) Japan (n=58)

01.May 22

01.58022

The original recruitment target was 300 patients over 5 years which was revised to 260 patients over 7 years, both to obtain 190 events. The actual recruitment is estimated to be around 105 patients. Using the same constraints as the original design (alpha=0.2, HR=0.775, 45% survival at 3 years, 2 year follow-up) without a formal interim analysis for futility and adjusting the accrual to the actual observed accrual over the past 5 years, it is likely that around 68 events would be observed at the end of a 2 year follow-up, which would yield around 58% power.

Question 2: Monotherapy versus Combination

The original recruitment target was 280 patients over 5 years which was revised to 240 patients over 7 years, both to obtain 190 events. The actual recruitment is estimated to be around 135 patients. Using the same constraints as the original design (alpha=0.2, HR=0.775, 40% survival at 3 years, 2 year follow-up) without a formal interim analysis for futility and adjusting the accrual to the actual observed accrual over the past 5 years, it is likely that around 98 events would be observed at the end of a 2 year follow-up, which would yield around 66% power.

7.3 Analytical Plan

7.3.1 Primary Efficacy Analysis

The following approach will be taken for both trial questions (Adjuvant question and Oxaliplatin question). The primary frequentist analysis will be a conventional analysis of DFS using Cox regression techniques in the ITT population. Assuming this result is statistical significant at 20% 1-sided level of

Version 6: 16th July 2021 Page 57 of 87

statistical significance this result is then combined with the clinicians prior to determine a final posterior distribution.

Example: Assume the result of the trial was **just** statistically significant at 1-sided 20% level. The table below shows the 95% predictive intervals for DFS HR, based on trial data alone, a postulated clinician prior and the combined posterior distribution.

	Estimate of DFS	Lower limit of	Upper limit of 95%
	hazard ratio	95% predictive	predictive interval
		interval	
Trial data alone	0.88	0.65	1.18
Clinician prior	0.78	0.60	1.01
Combined posterior	0.82	0.68	1.00
distribution			

As can be seen when combined with the clinician prior, the 95% predictive interval excludes the possibility of any negative impact.

7.3.2 Secondary Efficacy Analysis

Survival: Although the trial is not powered for OS the results for both the Adjuvant and Oxaliplatin questions in terms of OS will be examined by:

- (i) Estimating the observed OS HR from the trial.
- (ii) Predicting OS from DFS and other patient characteristics/interim observations for those patients still alive at the end of the trial and using these estimated survival times combined with the actual observed times to re-estimate the OS HRs for the two trial questions (15)
- (iii) Combining (ii) above with a clinician prior for the OS hazard ratio

7.3.3 Safety Analysis

The worst grade of CTCAE toxicity during the treatment period will be compared between the randomised arms for the Oxaliplatin question.

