Physical/Clinical Assessment (inc height and weight, BP, Pulse, assessment of neuropathy and assessment of sensorineural hearing impairment)		√		√	√										
Body Surface Area		✓													
ECG ⁽²⁾		√													
ECOG Performance Status		√													
Surgery ⁽³⁾	To be within 14 weeks of randomisation														
Laboratory Procedures		(/5)	T	1		T .	1	1	1						
Haematology (Co-ag) (4)		√ (5)													
Haematology (FBC)		√ (5)		√ (5)	√ (5)	√ (5)	√ (5)	√ (5)	√ (5)	√ (5)	√ (5)	√ (5)			
Urea & Electrolytes		√ (5)		√ (5)	√ (5)	√ (5)	√ (5)	√ (5)	√ (5)	√ (5)	√ (5)	√ (5)			
Liver Function Tests (7)		√ (5)		√ (5)	√ (5)	√ (5)	√ (5)	√ (5)	√ (5)	√ (5)	√ (5)	√ (5)			
Magnesium and estimated GFR		√ (5)													
Urine Pregnancy Test		✓													
Radiological Assessment															
CT Scan (chest, abdomen and pelvis) (8)	To be within 12 w entry						√ (9)		√ (9)		√ (9)				
Patient Questionnaires									•						
EORTC QLQ-C30 & CR29 QoL		√		√ (10)	✓	√ (10)	√	√	√						
EQ-5D		✓		√ (10)	✓	√ (10)	✓	✓	✓	✓	✓	✓			
Translational Research															
Tissue collection (11)	✓														
Blood Sample collection (12)		√													
DPD Deficiency Testing ⁽¹⁴⁾	✓														

Version 6: 16th July 2021

Schedule of Assessments – For patients randomised to 5-FU/FA +/- Oxaliplatin

	Scree	ening							Treatm	ent Cycl	е							Foll	ow Up			
Trial Procedures	≤28 days prior to Reg/Rand	≤7 days prior to Reg/Rand	Reg/Rand	Cycle 1	Cycle 2	Cycle 3	Cycle 4	Cycle 5	Cycle 6	Cycle 7	Cycle 8	Cycle 9	Cycle 10	Cycle 11	Cycle 12	Moth 9 post reg/rand	Moth 12 post reg/rand	Moth 18 post reg/rand	Moth 24 post reg/rand	Month 30 post reg/rando	Moth 36 post	Annually until 7 yrs post
Informed Consent (1)	_																					
Review of Eligibility Criteria		√																				
Medical History		· ✓																				
Physical/Clinical Assessment (inc height and weight, BP pulse, assessment of neuropathy and assessment of sensorineural hearing impairment)		√		√	*	~	*	√	√	√	~	√	*	√	*							
Body Surface Area		✓																				
ECG ⁽²⁾		√																				
ECOG Performance Status		✓		√	✓	√	√	√	√	√	√	√	✓	√	√							
Toxicity Assessment				✓	✓	✓	✓	✓	✓	✓	✓	✓	✓	✓	✓							
Administration of IMP ⁽¹³⁾				✓	✓	✓	✓	✓	✓	✓	✓	✓	✓	✓	✓							
Surgery ⁽³⁾	weeks o	vithin 16 of cycle 1 ate																				
Laboratory Procedures																						
Haematology (Clotting ⁽⁴⁾)		√ (5)		√ (6)	√ (6	√ (6)	√ (6)	√ (6)														

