Haematology (FBC)		√ (5)		√ (6)	√ (6	√ (6)	√ (6)	√ (6)	√ (6)	√ (6)	√ (6)	√ (6)	√ (6)	√ (6)	√ (6)							
Urea & Electrolytes		√ (5)		√ (6)	√ (6	√ (6)	√ (6)	√ (6)	√ (6)	√ (6)	√ (6)	√ (6)	√ (6)	√ (6)	√ (6)							
Liver Function Tests (7)		√ (5)		√ (6)	✓	√ (6)	√ (6)	√ (6)	√ (6)	√ (6)	√ (6)	√ (6)	√ (6)	√ (6)	√ (6)							
Magnesium and GFR		√ (5)		√ (6)	√ (6	√ (6)	√ (6)	√ (6)														
Urine Pregnancy Test		√ (5)																				
Radiological Assessment																						
CT Scan (chest, abdomen and pelvis) (8)	To be 12weeks	within pre-trial															√ (9)		√ (9)		√ (9)	
Patient Questionnaires																						
EORTC QLQ-C30 & CR29 QoL		✓							✓						✓	✓	✓	✓	✓			
EQ-5D		✓							✓						✓	✓	✓	✓	✓	✓	✓	✓
Translational Research																						
Tissue collection (11)	✓																					
Blood Sample collection (12)		✓																				
DPD Deficiency Testing ⁽¹⁴⁾	✓																					

Version 6: 16th July 2021

Schedule of Assessments – For patient randomised to Capecitabine +/- Oxaliplatin

	Screening			Treatment Cycle								Follow Up							
Trial Procedures	<pre>≤28 days prior to Reg/Rand</pre>	≤7 days prior to Reg/Rand	Reg/Rand	Cycle 1	Cycle 2	Cycle 3	Cycle 4	Cycle 5	Cycle 6	Cycle 7	Cycle 8	Moth 9 post reg/rand	Moth 12 post reg/rand	Moth 18 post reg/rand	Moth 24 post reg/rand	Moth 30 post reg/rand	Moth 36 post reg/rand	Annually until 7 yrs post reg/rand	
Informed Consent (1)	✓																		
Review of Eligibility Criteria		✓																	
Medical History		✓																	
Physical/Clinical Assessment (inc height and weight BP, pulse, assessment of neuropathy and assessment of sensorineural hearing impairment)		~		√	~	~	√	~	~	✓	✓								
Body Surface Area		✓																	
ECG ⁽²⁾		✓																	
ECOG Performance Status		✓		√	✓	√	√	√	√	√	√								
Toxicity Assessment				✓	✓	✓	✓	✓	✓	✓	✓								
Administration of IMP ⁽¹³⁾				✓	✓	✓	✓	✓	✓	✓	✓								
Surgery ⁽³⁾	To be with weeks of c date	ycle 1																	
Laboratory Procedures		((5)		(15)	((6)	((6)	((5)	(15)	((6)	((5)	((5)								
Haematology (Clotting ⁽⁴⁾)		√ (5)		√ (6)	√ (6)	√ (6)	√ (6)	√ (6)	√ (6)	√ (6)	√ (6)								
Haematology (FBC)		√ (5)		√ (6)	√ (6)	√ (6)	√ (6)	√ (6)	√ (6)	√ (6)	√ (6)	√ (6)	√ (6)	√ (6)	√ (6)	√ (6)	√ (6)	√ (6)	
Urea & Electrolytes		√ (5)		√ (6)	√ (6)	√ (6)	√ (6)	√ 6)	√ (6)	√ (6)	√ (6)	√ (6)	√ (6)	√ (6)	√ (6)	√ (6)	√ (6)	√ (6)	

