4.1.2 Evaluations While on Trial Treatment

Prior to each cycle of chemotherapy the following tests should be performed:

- ECOG performance status
- Toxicity Assessment (only toxicities which are grade 2 or above require entry to the CRF)
- If the patient has been randomised to receive oxaliplatin treatment clinical assessment of neuropathy should be performed at all study visits
- If the patient has been randomised to receive oxaliplatin treatment clinical assessment of sensorineural hearing impairment should be performed at all study visits
- Haematology blood sample (full blood count). From cycle 2 onwards pre-cycle bloods should be performed within 2 days of treatment. For patients on anti-coagulant therapy, appropriate clotting factors should be tested at each chemotherapy visit.
- Biochemistry including U&E, LFT, magnesium and calculated or measured GFR. From cycle 2 onwards pre-cycle biochemistry should be performed within 2 days of treatment
- QoL questionnaires when required EQ-5D and EORTC QLQ-C30 and CR29 (at 3 and 6 months post randomisation)

If a patient stops their allocated treatment early or if the patient experiences treatment delays the BALLAD UK follow-up visits will still be due as per the protocol schedule i.e. timed relative to date of randomisation. This is the required procedure even if the patient has experienced treatment delays and is still receiving chemotherapy treatment.

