5.10.3 Dose Modification for Neurosensory Toxicity

Neurosensory toxicity with these regimens is known to be a consequence of the oxaliplatin. Therefore reduction in this drug is the most important adjustment to make. The table below gives recommendations but is not meant to be prescriptive and dose adjustments according to local protocol may be followed as long as the dose given is carefully annotated in the CRF.

Regimen	Grade 1, or 2 (if Grade 2 persisting ≤7 days)	Grade 2 persisting >7 days	Grade 3	Grade 4
5-FU and Oxaliplatin	Full dose oxaliplatin	Reduce oxaliplatin dose by 25%	Discontinue oxaliplatin	Discontinue oxaliplatin
Capecitabine and Oxaliplatin	Full dose oxaliplatin	Reduce oxaliplatin dose by 25%	Discontinue oxaliplatin	Discontinue oxaliplatin

Acute dysasthesia of the larynx may be mitigated by slowing the rate of infusion of oxaliplatin.

If repeat events of neurosensory toxicity occur; local practice should be followed in terms of any dose reductions applied, with the management of the toxicities being fully documented in the patient's medical records.

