6.2.2 Recording of Adverse Events

Full details of AEs including the nature of the event, start and stop dates, severity, relationship to trial drug and outcome will be recorded in the patient's medical records. However, only AEs that are grade 2 or above require entry on the trial CRF. All AEs must be followed until they resolve or return to the baseline value, or if they do not resolve, for at least 30 days after discontinuation of trial medication or until they are confirmed as likely to never resolve. Perceived lack of efficacy is not an AE. An exacerbation of a pre-existing condition is an AE.

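### Protocol 4.1.2 and the schedules of assessments disagree on who is assessed for neuropathy and when, and neuropathy persisting after treatment is outside the stated oxaliplatin safety comparison

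*Protocol*

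**What the plan says.** Protocol 7.3.3 is one sentence: "The worst grade of CTCAE toxicity during the treatment period will be compared between the randomised arms for the Oxaliplatin question". It gives no comparison for the period after treatment.

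Protocol 4.1.2 lists what is done before each cycle. One item applies to everyone on chemotherapy: "Toxicity Assessment (only toxicities which are grade 2 or above require entry to the CRF". The neuropathy item is conditional: "If the patient has been randomised to receive oxaliplatin treatment clinical assessment of neuropathy should be performed at all study visits". A parallel item sets the same condition for sensorineural hearing impairment.

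The schedules of assessments use one table for 5-FU/FA with or without oxaliplatin and one for capecitabine with or without oxaliplatin. In both, the physical assessment row includes the two checks. The capecitabine table words it as "BP, pulse, assessment of neuropathy and assessment of sensorineural hearing impairment". The row is ticked at screening and at every cycle (12 for 5-FU/FA, 8 for capecitabine), with no tick in any follow-up column. The toxicity row is ticked at every cycle and is also empty in follow-up.

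Section 6.2.2 puts adverse events of grade 2 or above on the CRF and requires them to be followed to resolution or baseline or, if unresolved, "for at least 30 days after discontinuation of trial medication or until they are confirmed as likely to never resolve". Section 5.10.3 states: "Neurosensory toxicity with these regimens is known to be a consequence of the oxaliplatin".

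**The concern.** The oxaliplatin question is open-label, and neurosensory toxicity is the harm that the protocol itself attributes to the added drug. A between-arm comparison of that harm needs the same examination, on the same timetable, in both arms. Section 4.1.2, read alone, asks for the dedicated examination in one arm only. The schedules ask for it in both. A site could follow either in good faith.

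There is a second, separate problem. A worst grade during treatment does not distinguish an episode that resolves from one that lasts, although the dose table in 5.10.3 itself turns on persistence at grade 2. Toxicity is a secondary objective (2.2), neurotoxicity is a named target of the translational work (4.2), and adverse events enter the lifetime cost-effectiveness model (7.3.5). How long neuropathy lasts is therefore relevant to several stated uses of the data.

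The two problems act differently. Unequal examination would overstate the oxaliplatin excess on treatment. The cut-off at the end of treatment leaves late or lasting excess out of the comparison.

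**Working it through.** There is no stated figure to reproduce, so this is a comparison of texts with simple arithmetic.

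**1. Who is assessed, and when**

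| Source | Monotherapy arm | Oxaliplatin arm | After treatment |
|---|---|---|---|
| 4.1.1, baseline | yes | yes | not applicable |
| 4.1.2, dedicated neuropathy and hearing checks | not asked for | yes | all study visits, read literally |
| Schedules, same checks | every cycle | every cycle | no tick |
| 4.1.2 and schedules, general toxicity assessment | every cycle | every cycle | no tick |
| 6.2.1, adverse event questioning | each trial visit | each trial visit | each trial visit |

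Rows two and three conflict twice: on the arm, and on whether follow-up is included.

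**2. Size of the ascertainment risk**

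Let p be the true monotherapy rate of grade 2 or higher neuropathy and s the share of it detected, with full detection in the oxaliplatin arm. The observed difference is p_ox − s·p and the true difference is p_ox − p. The overstatement is therefore p × (1 − s). The protocol gives no rates, so p and s are assumptions. Appendix 2 lists numbness or tingling for capecitabine, usually with hand-foot syndrome, so p need not be zero.

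| p | s = 1 | s = 0.5 | s = 0 |
|---|---|---|---|
| 2% | 0 | 1.0 point | 2 points |
| 5% | 0 | 2.5 points | 5 points |
| 10% | 0 | 5.0 points | 10 points |

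The column s = 1 corresponds to sites following the schedules. The column s = 0 is an extreme, because the general toxicity assessment would have to miss every case.

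**3. Where scheduled grading ends**

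The last pre-cycle check, counted from cycle 1 without delays, is at (cycles − 1) × cycle length:

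- two-weekly regimen: (12 − 1) × 2 = week 22
- three-weekly regimen: (8 − 1) × 3 = week 21

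The next scheduled visit is month 9 after randomisation, with neither row ticked. The treatment period is 168 days (24 × 7) out of 7 × 365.25 = 2,557 days of maximum follow-up, or 6.6%.

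**4. Whether adverse event follow-up bridges the gap**

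Allow 14 days from randomisation to cycle 1 (the schedule footnote), 168 days of treatment and the 30-day minimum in 6.2.2. That gives 14 + 168 + 30 = 212 days, or 212 / 30.44 = about 7.0 months from randomisation. For a 26-week regimen it is 14 + 182 + 30 = 226 days, or about 7.4 months. Both fall before month 9. The alternative end point in 6.2.2, confirmation that the event is unlikely ever to resolve, permits follow-up to stop for exactly the lasting cases.

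**5. Whether the questionnaires bridge it**

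QLQ-C30 and CR29 run to 24 months and EQ-5D to 84 months (4.1.4). The forms printed in Appendices 5 and 6 contain no numbness or tingling item, so they reflect neuropathy only through function, pain or general health.

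**The case against.** The strongest reply is that 4.1.2 adds emphasis for oxaliplatin patients and exempts nobody. The same list requires a toxicity assessment before every cycle without regard to arm, everyone is assessed at baseline, and the schedules include both arms. This largely stands. A reader might infer from 4.1.2 that the comparison is biased because one arm goes unexamined. The documents do not support that: unequal ascertainment is a risk that depends on which text a site follows, and it is zero under the schedules.

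A reader might also infer that lasting harm is unmeasured. That too goes beyond the documents. Adverse events are asked about at each trial visit (6.2.1) and followed (6.2.2), late related serious events are reportable (6.3), and EQ-5D is compared between arms up to 7 years (7.3.5). What is missing is systematic grading of neuropathy after treatment and a stated comparison of it.

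A third reply is that worst grade on treatment is a legitimate summary and that further analyses may sit in a SAP not shown here. That is fair for the analysis. It does not answer the data point, because a SAP cannot supply grades that were never systematically collected.

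Finally, it is tempting to halve the projected 135 patients in 7.2 and claim the precision of about 67 per arm for a 12-month comparison. That total is for GLOBAL BALLAD. This protocol governs BALLAD UK only, and partner trials run under their own protocols. The recruitment figure for the adjuvant question shows 10 UK patients of 77. No precision is claimed here.

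**Conclusion.** The point holds as a contradiction with two limited consequences.

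- Section 4.1.2 and the schedules must be reconciled on arm and on follow-up visits. Until then the oxaliplatin safety comparison carries a risk of differential ascertainment: none if the schedules are followed and, if 4.1.2 is followed, an overstatement of 1.0 to 5.0 points for assumed monotherapy rates of 2% to 10% with half detected. General toxicity grading limits this.
- Neuropathy that persists after treatment is not systematically graded beyond about week 21 or 22 and is not in the comparison stated in 7.3.3. Other sources capture part of it, unsystematically or indirectly.

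The DFS analysis is unaffected. The change is worth making because it is cheap and because follow-up grades not recorded at the visit are hard to recover.

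**What to change.** 1. Reconcile 4.1.2 with the schedules so that neuropathy and hearing are CTCAE-graded identically in both arms of the oxaliplatin question at every cycle and at existing follow-up visits, for example months 9, 12, 18, 24, 30 and 36. Add the matching ticks to both chemotherapy schedules.
2. In 7.3.3, keep the treatment-period worst grade and add a between-arm comparison of grade 2 or higher neuropathy at 12 months.
3. Ask the partner trials, through the GLOBAL BALLAD TSC, whether they can collect the same field.

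The cost is one CRF field at visits already scheduled, with no new visits and no change to treatment or sample size. Patients already past those visits will have missing values, which should be reported. Without the partner trials, the 12-month comparison rests on BALLAD UK alone and will be imprecise.
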